## 10 STUDY OVERSIGHT

A summary of DSMC activities is as follows:

- Reviews all clinical trials conducted at the UWCCC for subject safety, protocol compliance, and data integrity.
- Reviews Adverse Events recorded by study team as described in section 9.4.
- Reviews all Serious Adverse Events (SAE) requiring expedited reporting, as defined in the protocol, for all clinical trials conducted at the UWCCC, and studies conducted at external sites for which the UWCCC acts as an oversight body.
- Reviews all reports generated through the UWCCC DSMS elements (Internal Audits, Quality Assurance Reviews, Response Reviews, Compliance Reviews, and Protocol Summary Reports) described in Section II of this document.
- Notifies the protocol PI of DSMC decisions and, if applicable, any requirements for corrective action related to data or safety issues.
- Notifies the Clinical Research Committee (CRC) of DSMC decisions and any correspondence from the DSMC to the protocol Principal Investigator.
- Works in conjunction with the UW Health Sciences IRB in the review of relevant safety information as well as protocol deviations, non-compliance, and unanticipated problems reported by the UWCCC research staff.
- Ensures that notification of SAEs requiring expedited reporting is provided to external sites participating in multi-institutional clinical trials coordinated by the UWCCC.

### Monitoring and Reporting Guidelines

UWCCC quality assurance and monitoring activities are determined by study sponsorship and risk level of the protocol as determined by the PRMC. All protocols (including Intervention Trials, Non-Intervention Trials, Behavioral and Nutritional Studies, and trials conducted under a Training Grant) are evaluated by the PRMC at the time of committee review. UWCCC monitoring requirements for trials without an acceptable external DSMB are as follows:

- **Intermediate Monitoring**

Protocols subject to intermediate monitoring generally include UW Institutional Phase I/II and Phase II Trials. These protocols undergo review of subject safety at regularly scheduled DOT meetings where the results of each subject's

treatment are discussed and the discussion is documented in the DOT meeting minutes. The discussion includes the number of subjects enrolled, significant toxicities, dose adjustments, and responses observed. Protocol Summary Reports are submitted on a bi-annual basis by the study team for review by the DSMC.

## Review and Oversight Requirements

- Study Progress Review
  - Protocol Summary Reports (PSR) are required to be submitted to the DSMC in the timeframe determined by the risk level of the study (quarterly; semi-annually; or annually). The PSR provides a cumulative report of SAEs, as well as instances of noncompliance, protocol deviations, and unanticipated problems, toxicities and responses that have occurred on the protocol in the timeframe specified. PSRs for those protocols scheduled for review are reviewed at each DSMC meeting.
  - Protocol Summary Reports enable DSMC committee members to assess whether significant benefits or risks are occurring that would warrant study suspension or closure. This information is evaluated by the DSMC in conjunction with other reports of quality assurance activities (e.g., reports from Internal Audits, Quality Assurance Reviews, etc.) occurring since the prior review of the protocol by the DSMC. Additionally, the DSMC requires the study team to submit external DSMB or DSMC reports, external monitoring findings for industry-sponsored studies, and any other pertinent study-related information.
  - In the event that there is significant risk warranting study suspension or closure, the DSMC will notify the PI of the DSMC findings and ensure the appropriate action is taken for the protocol (e.g., suspension or closure). The DSMC ensures that the PI reports any temporary or permanent suspension of a clinical trial to the appropriate agencies. DSMC findings and requirements for follow-up action are submitted to the CRC.

## 11 CLINICAL SITE MONITORING

Clinical site monitoring is conducted to ensure that the rights of human subjects are protected, that the study is implemented in accordance with the protocol and/or other operating procedures, and that the quality and integrity of study data and data collection methods are maintained. Monitoring for this study will be performed by NIDCR's Clinical Research Operations and Management Support (CROMS) contractor. The monitor will evaluate study processes and documentation based on NIDCR standards and the International Conference on Harmonisation (ICH), E6: Good Clinical Practice guidelines (GCP).

Details of clinical site monitoring will be documented in a Clinical Monitoring Plan (CMP) developed by the CROMS contractor, in collaboration with the NIDCR Office of Clinical Trials and Operations Management (OCTOM) and the NIDCR Program Official. The CMP will specify the frequency of monitoring, monitoring procedures, the level of clinical site monitoring activities (e.g., the percentage of subject data to be reviewed), and the distribution of monitoring reports. Some monitoring activities may be performed remotely, while others will take place at the study site(s). Staff from the CROMS contractor will conduct monitoring activities and provide reports of the findings and associated action items in accordance with the details described in the CMP. Documentation of monitoring activities and findings will be provided to the site study team, the study PIs, OCTOM, and the NIDCR. The NIDCR reserves the right to conduct independent audits as necessary.

## 12 STATISTICAL CONSIDERATIONS

### 12.1 Study Hypotheses

The primary objective of this window of opportunity trial is to test the hypotheses that elevated AXL and HER3 can predict cetuximab resistance (CTXR) in head and neck cancer patients. Following informed consent, tumor tissue from the pre-treatment/research biopsy will be obtained for further analysis. The participant will then receive two weekly doses of cetuximab during the interval between research biopsy and surgery, ensuring that no delay in standard of care (SOC) will occur. At the time of surgery, additional tumor tissue will be obtained for study analysis.

Correlative studies will include the measurement of AXL and HER3 expression from the pre-treatment/research biopsy as well as collection of circulating tumor cells. Tissue from the pre-treatment/research biopsy will be utilized for patient-derived xenograft (PDX) development.

### 12.2 Sample Size Considerations

We plan to enroll 36 HNSCC patients, powered on the basis of the primary study endpoint: the clinical response rate to cetuximab according to RECIST criteria in low AXL vs. high AXL patients (measured using VECTRA/inForm software). Previous data show that 1 in 3 patients respond to cetuximab, and about one-third (21/57 or 37%) of HNSCC patients have high AXL expression. This sample size is based on 90% power to detect a difference between a response rate of 20% in the high AXL (2+ or 3+) group vs. 65% in the low AXL (0 or 1) group, with an expected ratio of 2:1 low vs. high AXL expression participants. One-sided type I error was fixed at 5%.

For evaluation of safety endpoints, any participant that undergoes a research biopsy will be included. For evaluation of efficacy, molecular/correlative studies, and creation of PDXs, participants must receive both cetuximab doses in their

entirety and have surgical resection of the tumor. If a participant is unevaluable for these endpoints, then the patient will be replaced at the discretion of the principal investigator.

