### **12.4 Final Analysis Plan**

#### **Analysis of Primary Endpoints**

The relationship between AXL expression as a continuous variable with clinical response will be analyzed using the Wilcoxon rank sum test.

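### Section 12.2 pairs 90% power with a one-sided error fixed at 5%, but no test that holds 5% exceeds 84.9% power with 24 low-AXL and 12 high-AXL patients

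*Combined protocol and SAP*

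**What the plan says.** Section 12.2 (Sample Size Considerations) opens: "We plan to enroll 36 HNSCC patients, powered on the basis of the primary study endpoint", which it describes as the RECIST response rate in low versus high AXL patients. It continues: "This sample size is based on 90% power to detect a difference between a response rate of 20% in the high AXL" category, meaning scores of 2+ or 3+. The comparator is given as "group vs. 65% in the low AXL (0 or 1) group". The assumed split between the two categories is then stated: "with an expected ratio of 2:1 low vs. high AXL expression participants". On the error rate it says: "One-sided type I error was fixed at 5" per cent. The ratio rests on the statement that "about one-third (21/57 or 37%) of HNSCC patients have high AXL expression". The section names neither a test nor a formula for this comparison.

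Section 12.4 plans a different primary analysis: "The relationship between AXL expression as a continuous variable with clinical response will be analyzed using the Wilcoxon rank sum test". It gives no power for that test.

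**The concern.** The sentence in 12.2 states two properties of one comparison: power of 90%, and a one-sided error held at 5%. With 24 and 12 patients and a binary outcome, large-sample formulas can depart noticeably from what a test actually delivers. If the two properties cannot both hold at this size, the trial's only quantitative justification for 36 patients overstates the design. The practical risk lies in reading a null result: a reader would take the chance of missing a true 65% versus 20% difference to be 10%, when for any test that keeps the stated error rate it is larger.

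**Working it through.** **Inputs, all from section 12.2.** Response 0.20 in high AXL and 0.65 in low AXL (difference 0.45); low:high 2:1, so 12 high and 24 low at N=36; one-sided 5% (z = 1.645); power 90% (z = 1.282).

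**1. Reproducing the plan's figure.** The unpooled-variance formula for the smaller group is

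n_high = (1.645 + 1.282)² × [0.20×0.80 + (0.65×0.35)/2] / 0.45² = 8.564 × 0.27375 / 0.2025 = 11.58, rounded up to 12.

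Adding 24 low-AXL patients gives 36, an exact match. The nominal power at 12/24 uses SE₁ = √(0.65×0.35/24 + 0.20×0.80/12) = 0.1510:

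Φ(0.45/0.1510 − 1.645) = 90.9%.

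The other standard one-sided formulas tried do not return 36. The pooled-variance formula has SE₀ = √(0.5×0.5×(1/24 + 1/12)) = 0.1768 and gives Φ((0.45 − 1.645×0.1768)/0.1510) = 85.4% at N=36, or 42 patients for 90%. The arcsine formula gives 85.0% and about 43 patients. The pooled formula with continuity correction gives 54.

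**2. What tests deliver at 24/12.** All 25 × 13 = 325 possible tables were enumerated. Power is the total probability of the rejected tables at 65%/20%. True size is the largest rejection probability over all common response rates.

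| Test (nominal one-sided 5%) | Exact power | True maximum size |
|---|---|---|
| Wald (unpooled z) | 88.3% | 12.9% |
| Pooled z | 87.9% | 6.3% |
| Boschloo | 82.9% | 4.7% |
| Exact unconditional, pooled z | 82.0% | 4.2% |
| Fisher exact | 74.6% | 2.4% |

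The Wald test, which is the one that matches the formula behind 36, has true error of 6.5% at a common response rate of 50%, 8.1% at the 1 in 3 quoted in 12.2, and its maximum at a rate of about 11%.

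**3. A ceiling that does not depend on the choice of test.** Power at 65%/20% was maximised by linear programming over every possible rejection rule, randomised rules included, subject to error of at most 5% across a grid of common response rates from 1% to 99%. The maximum is 84.9% at 24/12. Constraining only the grid points can only raise this value, so it is a valid upper bound.

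**4. Sensitivity to the split.** Section 12.2 also cites 21/57 = 37% high AXL, which is about 13 high and 23 low at N=36. There Fisher gives 77.4%, the exact unconditional test 85.0%, Boschloo 85.5%, and the ceiling is 86.3%. These are still below 90%.

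**The case against.** The strongest reply is that nothing was miscalculated. The unpooled formula is standard, the plan's inputs put through it give 36 exactly, and preferring the pooled formula would be a matter of taste. That stands. A reader might infer from the pooled formula's 85% that 36 is an arithmetic error, or that the trial needs 42 patients. The documents support neither. The 36 comes from a recognised formula, and 42 would not secure 90% with tests that hold 5% either: at 28/14 Fisher gives 82.8%, the exact unconditional test 85.2% and Boschloo 88.6%. Nor would it help to write 85% into the plan, since that is another normal approximation; the pooled z test itself enumerates to 87.9% power with size up to 6.3%.

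A second reply is that the shortfall is small if a slightly liberal test is accepted. This is partly right. The two approximate tests miss a true difference about 12% of the time, and the pooled z test has true error of only about 5.1% at a response rate of 1 in 3. The 25% miss risk belongs to Fisher's test alone, whose true size is about half the nominal level. But 12.2 says the error was fixed at 5%, and the approximate tests do not keep to that at every response rate.

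A third reply is that the planned primary test is a Wilcoxon on continuous AXL, so none of these powers describes it. That is correct, and it limits the point to the comparison that 12.2 describes. It does not support the 90%, because no power is stated for the Wilcoxon test. The documents do not allow that power to be calculated without assuming a distribution for AXL.

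**Conclusion.** The point holds as a misstated operating characteristic, not as an arithmetic error. At N=36 the stated combination of 90% power and a 5% one-sided error is not available from any test of 65% versus 20%: the ceiling is 84.9% at 24/12 and 86.3% at 23/13. Named tests that hold 5% give 74.6% to 82.9% at 24/12, so their miss risk is about 17% to 25% against the stated 10%.

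This takes the plan's response rates as given and assumes 36 evaluable patients. The section adds no allowance for dropout and says of an unevaluable patient: "then the patient will be replaced at the discretion of the principal investigator". AXL status is observed rather than allocated, so the realised split may differ from both splits examined. The conclusion concerns the low versus high AXL response-rate comparison only and says nothing about the power of the section 12.4 analysis.

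**What to change.** In section 12.2, keep N=36 and:

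- state that it was obtained from the unpooled-variance normal approximation;
- replace the 90% with the exact power of a named test that holds one-sided 5%, for example about 83% with Boschloo's test or 75% with Fisher's exact test at 24 low and 12 high;
- say that this figure refers to the response-rate comparison between low and high AXL groups and not to the Wilcoxon rank sum test in section 12.4.

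This changes a sentence or two. It asks for no extra patients and changes neither conduct nor analysis. The only cost is a less favourable stated power.

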### Research-related Biopsies and Blood Draws

Research-related procedures include a separate research biopsy of the tumor at the time of the diagnostic biopsy for analysis of Ki67, putative markers of CTX sensitivity, and research-related blood draws for collection of circulating tumor cells at five timepoints: screening visit, within 24 hours prior to surgery, and at follow-up visits: approximately 1 month post-surgery, as well as approximately 3 and 12 months post definitive care. The tissue obtained for research biopsy will be placed in culture media or saline and provided to the biologic correlate study team. If pathology confirms a diagnosis other than HNSCC, the patient will be removed from the study, and the research biopsy tissue will be released to the University of Wisconsin Translational Science BioCore (TSB) Biobank. If the clinical biopsy is inconclusive, the research tissue will be released back to University of Wisconsin Surgical Pathology department to aid in a clinical diagnosis. The research-related blood draws will be given directly to the biologic correlate study team for quantification of circulating tumor cells and/or other biomarkers.

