### **5 STUDY ENROLLMENT AND WITHDRAWAL**

This study is anticipated to enroll a target sample size of 36 subjects. We estimate approximately 100 subjects will be screened to reach the target enrollment.

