## 5.1 Subject Inclusion Criteria

Adult men and women and members of all races and ethnic groups are eligible for this trial. Persons with impaired decision-making capacities will not be eligible for enrollment in this study. Eligibility criteria will be assessed via clinical labs, review of medical records as well as self-reporting. Subjects will be recruited from the University of Wisconsin Hospital and Clinics.

Step 1 registration will occur when subject has signed consent and consent has been registered (added) to ONCORE.:

- Age  $\geq$  18 years
- Informed consent: patients must be informed of the investigational nature of the study and must be able to sign a written informed consent.
- Inclusion criteria for research biopsy (screen)
  - Patients must have suspected or known clinical presentation of head and neck squamous cell carcinoma or a recurrence of head and neck squamous cell carcinoma after initial therapy. For newly suspected head and neck cancer, the procedure will obtain tissue for both standard of care biopsy and additional tissue for research.
  - Participants must have sufficient tumor volume (approximately 10 cc) to accommodate at minimum 2-3 core samples for the research biopsy. This will be approximated based on clinical evidence, such as physician visualization or palpitation.
  - Patients are required to consent to the TSB Biobank protocol (2016-0934) as part of this study.
  - Surgical management must be the chosen modality for management of the head and neck squamous cell cancer.
    - Other therapeutic modalities may follow, but surgery must be the choice for first therapy rendered.

For Step 2 enrollment on this study an individual must meet all criteria for Step 1 and the following criteria:

- Inclusion criteria for cetuximab treatment:
  - Patients must have a biopsy proven, squamous cell carcinoma of the head and neck, excluding advanced cutaneous head and neck squamous cell carcinoma.
  - ECOG performance status  $\leq$  1
  - Women of childbearing potential (WOCP) must not be pregnant (confirmed by a negative urine/serum pregnancy test within 7 days of cetuximab treatment). In addition, a medically acceptable method of birth control must be used such as an oral, implantable, injectable, or transdermal hormonal contraceptive, an intrauterine device (IUD), use of a double barrier method (condoms, sponge, diaphragm, or vaginal ring

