  - history of arterial or venous thrombosis/thromboembolic event, including pulmonary embolism within 6 months of study enrollment
  - any condition requiring the use of immunosuppression, excluding rheumatologic conditions treated with stable doses of corticosteroids
  - Use of herbal supplements (St. John's Wort, gingko biloba, etc.) within one week of cetuximab treatment

For patients who do not meet eligibility criteria for Step 2 of the study, the tissue from the research biopsy will be released to the TSB Biobank or back to surgical pathology if needed for a clinical diagnosis.

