### **5.5.2 Handling of Subject Withdrawals or Subject Discontinuation of Study Intervention**

If a subject decides to withdraw from the study (and not just from protocol therapy) all efforts should be made to complete and report study assessments as thoroughly as possible. The study team should contact the subject or a responsible relative by telephone to establish as completely as possible the reason for the study withdrawal. A complete final evaluation at the time of the subject's study withdrawal should be made with an explanation of why the

subject is withdrawing from the study. If the reason for removal of a subject from the study is an adverse event, it will be recorded on the eCRF.

If a subject is unevaluable for safety and efficacy endpoints (i.e., lacks molecular/correlative studies, and creation of PDXs, subject has not received both cetuximab doses in their entirety and/or has not had surgical resection of the tumor), then the subject will be replaced at the discretion of the principal investigator.

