#### **Analysis of Secondary Endpoints**

The safety of pre-operative cetuximab, as evaluated by hospital re-admissions for wound care or surgical complications attributed to cetuximab within 28 days after surgery, will be reported as a proportion including an exact 95% confidence interval.

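### The safety set in 12.2 counts biopsied patients who never receive cetuximab or surgery, which biases the re-admission proportion downward; 5.5.2 contradicts it and 12.4 names no denominator

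*Combined protocol and SAP*

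**What the plan says.** Three sections bear on who is counted for safety.

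- **Section 12.2** sets the inclusion rule: "For evaluation of safety endpoints, any participant that undergoes a research biopsy will be included". It requires both full cetuximab doses and resection only for efficacy, molecular/correlative studies and PDX creation. Its replacement sentence refers back to that second list: "If a participant is unevaluable for these endpoints, then the patient will be replaced at the discretion of the principal investigator".
- **Section 5.5.2** has a matching replacement rule, but it opens "If a subject is unevaluable for safety and efficacy endpoints" and applies the same condition (both full doses, resection) to safety as well.
- **Section 12.4, Analysis of Secondary Endpoints**, says that "hospital re-admissions for wound care or surgical complications attributed to cetuximab within 28 days after surgery, will be reported as a proportion" with an exact 95% confidence interval. It names no analysis set.

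The two-step design determines who has been biopsied. Step 1 in 5.1 admits patients on suspicion alone: "Patients must have suspected or known clinical presentation of head and neck squamous cell carcinoma". Section 4 provides that "If pathology confirms a diagnosis other than HNSCC, the patient will be removed from the study". Section 5.2 covers those who are biopsied and then fail Step 2: "For patients who do not meet eligibility criteria for Step 2 of the study, the tissue from the research biopsy will be released". Section 5 adds: "We estimate approximately 100 subjects will be screened to reach the target enrollment", the target being 36.

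**The concern.** The secondary endpoint can occur only in someone who received cetuximab and then had surgery. A set defined by the biopsy also contains people who did neither. They add to the denominator and can never add to the numerator, so the reported re-admission proportion is too low.

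The conflict with 5.5.2 works differently. A patient who stops after one dose, or part of one, and then has surgery is in the safety evaluation under 12.2 but unevaluable for safety under 5.5.2. Such patients are unlikely to be a random subset, because 6.2.1 and 6.3 tie discontinuation to toxicity. Leaving them out could move the rate either way.

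At stake is the trial's only secondary endpoint, which is its measure of the safety of giving cetuximab before surgery. Two analysts following different sections could report different rates from the same data.

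**Working it through.** **Plan's own figure.** The documents give no expected rate, precision or denominator for the re-admission endpoint, so there is nothing to reproduce. The documents supply 36 (target, 12.2) and about 100 (screened, section 5).

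**Step 1: direction under 12.2.** Let T be the number who received cetuximab and had surgery, B the number biopsied, and x the number with the event. All x events come from the T patients, so

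reported proportion = x/B = (x/T) × (T/B), with T/B ≤ 1.

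The bias is zero only if every biopsied participant is treated and operated. Otherwise it is downward.

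**Step 2: size under 12.2.** B is not stated. Assume T = 36. Then B is at least 36, and about 100 is a ceiling, since some of those screened may never be biopsied. The values 45 and 60, and the event counts, are assumptions for illustration. Intervals are Clopper-Pearson 95%.

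| Biopsied (B) | Factor 36/B | 5 events | Upper limit with 0 events |
|---|---|---|---|
| 36 (no attrition) | 1.00 | 5/36 = 13.9% (4.7-29.5%) | 9.7% |
| 45 | 0.80 | 5/45 = 11.1% (3.7-24.1%) | 7.9% |
| 60 | 0.60 | 5/60 = 8.3% (2.8-18.4%) | 6.0% |
| 100 (ceiling) | 0.36 | 5/100 = 5.0% (1.6-11.3%) | 3.6% |

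Even with no events, the upper limit falls as untreated patients are added.

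**Step 3: the two replacement rules side by side.**

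| | 12.2 | 5.5.2 |
|---|---|---|
| Endpoints that need both doses and resection | efficacy, molecular/correlative, PDX | safety and efficacy |
| Patient who stopped after dose 1, then had surgery | counted for safety | unevaluable for safety, may be replaced |

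Section 5.5.2 does not say that replaced subjects leave the safety analysis, so their exclusion is a risk and not a certainty.

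**Step 4: size if 5.5.2 were read as an exclusion.** Assume 40 treated and operated, 4 of them incompletely dosed and replaced, and 5 events in all.

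- Everyone kept: 5/40 = 12.5% (4.2-26.8%).
- The 4 left out, none with an event: 5/36 = 13.9% (4.7-29.5%).
- The 4 left out, two with an event: 3/36 = 8.3% (1.8-22.5%).

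**The case against.** **12.2 governs, and 5.5.2 is only a replacement rule.** Section 5.5.2 sits in a withdrawal section, its operative verb is to replace, and its list of criteria begins with the correlative and PDX items of 12.2, so the word safety there may be a drafting slip. That is plausible, and it is why exclusion is put only as a risk. The wording still contradicts 12.2. If 12.2 does govern, the diluted denominator is the one that applies.

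**Participant may mean a Step 2 enrollee.** Section 5.1 separates Step 1 registration from Step 2 enrollment, and section 4 removes non-HNSCC patients from the study. On that reading, dilution is limited to enrolled patients who are not treated or not operated. It would be smaller but in the same direction. The reading also fits poorly with 5.3.1, which pays participants after the biopsy, and with 12.2, which ties inclusion to the biopsy and not to enrollment.

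**The size is hypothetical.** This stands. Neither the event counts nor the number biopsied is in the documents. The ceiling of 100 is remote, because 5.1 requires sufficient tumor volume, surgery as first therapy and biobank consent before the biopsy. With few events the shift is small: 1/36 = 2.8% (0.1-14.5%) against 1/45 = 2.2% (0.1-11.8%).

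**The analysis is descriptive.** Also true: no hypothesis or threshold depends on this proportion, and a reader given the numbers treated and operated could recompute it. That limits the consequence but does not make the stated rule right.

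**An all-biopsied set has a proper use.** It does, for biopsy harms (9.1) and for events recorded from consent (9.2). The fault lies in using it for every safety endpoint.

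**Conclusion.** The concern holds. The direction follows from the endpoint definition and the two-step design: applied as written, 12.2 can only lower the re-admission proportion and its upper limit. The size depends on the unstated number biopsied. With 36 treated and operated, the multiplying factor is 1.0 with no attrition, 0.80 at 45 biopsied, 0.60 at 60, and 0.36 at the ceiling of 100. The contradiction between 12.2 and 5.5.2 is in the text itself, but whether it would remove anyone from the safety summaries is uncertain. Section 12.4 does not resolve either point. The primary endpoint is not affected. The correction should be made before analysis, because choosing a denominator after the events are known is what a plan should prevent.

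**What to change.** Name the analysis set for each safety endpoint in 12.2, and repeat it in 12.4 for the re-admission proportion:

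- biopsy-related events: all participants who had a research biopsy;
- AEs and SAEs on cetuximab: all who received any cetuximab;
- re-admission within 28 days after surgery: all who received any cetuximab and had surgery. Report alongside it the number treated who did not reach surgery, since this set leaves them out.

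In 5.5.2, remove safety from the unevaluable rule so that it matches 12.2, and state that replaced subjects stay in the safety analyses.

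The cost is protocol wording only. No new data, visits or patients are needed, and no clinical rule changes. The reported re-admission rate may be less favourable than under 12.2 as it stands.
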